**Table 3 : Storage Instructions :**

Between 2°C - 25°C.

Permitted temperatures: not limited between > 25°C and ≤ + 30°C, 15 days between > + 30°C and ≤ + 40°C, less than 5 days between 40°C and ≤ + 60°C, less than 5 days between > - 18°C and ≤ + 2°C.

Temperature logs should be kept updated by the pharmacist, to document adequate storage during the trial.

The investigator/pharmacist must ensure that the investigational product is administrated only to patients enrolled in this trial. The investigational product must not be used outside the context of the trial protocol.

The pharmacist or the authorized staff must document the receipt, the dispensation, and the return or destruction of all investigational products received during this trial. Records on investigational products delivery to the center, the inventory at the center, the use by each patient, and the return to the sponsor or destruction by the site must be implemented and maintained by the pharmacist or another appropriately trained individual at the investigational center. Will be reported on these records at least dates, quantities, batch numbers of the investigational products. Forms will be provided by the sponsor to ensure trial treatment accountability.

The pharmacist will implement an accounting of medicinal products dispensed, used and unused.

This process will be monitored by the ICM CRA during the trial. The CRA will check that the accountability documentation has been filled in and signed by the pharmacist before the investigational products, used and unused, are destroyed.

The destruction will take place in the investigator centers under the responsibility of their pharmacist in accordance with national regulatory requirements, and with prior formal agreement from the sponsor. A certificate of destruction, identifying concerned products, will be given to the sponsor.

## 6.4 Treatment duration

12 cycles have to be delivered consecutively or not.

Indeed, treatment can be temporarily stopped to perform surgical resection or regional procedures (radiofrequency, cryoablation, radiation therapy) if the disease become accessible to them but if it happens, before the end of the 12 planned cycles, the treatment

has to be resumed within 4 to 8 weeks after the loco-regional procedure has been completed in order to reach a total number of 12 cycles delivered.

If a surgery or a regional procedure is considered, we recommend respecting a time period of 4 weeks between the last chemotherapy and the procedure.

After 12 cycles, patients whose metastases are not progressing and are still unresectable will receive regorafenib (experimental regimen and at the same dose) until progression or toxicity.

## 6.5 Expected Toxicities

The expected adverse events of Oxaliplatin, 5 FU and Irinotecan are described in the respective Summaries of Product Characteristics (SmPC). Refer to the latest current version on the public drug database website (appendix 7) for:

- Elvorin
- 5 FU
- OXALIPLATINE
- IRINOTECAN

Refer to the latest investigator's brochure for Regorafenib.

## 6.6 Dose modification and Dose delay

### FOLFIRINOX

**Table 4 : Hematological criteria for dose modification/interruption of Folfirinox**

CBC on D15	CYCLE DELAY	DOSE REDUCTION			
		Irinotecan (CPT-11)	Oxaliplatin (L-OHP)	LV5FU**	
PNN $\geq 1.5 \times 10^9/l$ and plat. $\geq 100 \times 10^9/l$	No cycle delay	no dose reduction			
PNN $< 1.5 \times 10^9/l$	Treatment delayed until PNN $\geq 1.5 \times 10^9/l$ (until D29 if necessary).  In case of no recovery on D29, treatment stop, *	1st episode: dose reduction to 120 mg/m  2nd episode: maintain dose at 120 mg/m  3rd episode: treatment stop	1st episode: no dose reduction 2nd episode: reduce dose to 60 mg/m  3rd episode: treatment stop	1st episode: no dose reduction 2nd episode: no dose reduction 3rd episode: treatment stop	
Plat. $< 100 \times 10^9/l$	Delay treatment until recovery (plat. $\geq 100 \times 10^9/l$ ).  If no recovery on D29, treatment stop	1st episode: no dose reduction 2nd episode: reduce dose to 120 mg/m  3rd episode: treatment stop	1st episode: reduce dose to 60 mg/m  2nd episode: maintain dose at 60 mg/m  3rd episode: treatment stop	1st episode: no dose reduction 2nd episode: reduce the dose by 25% 3rd episode: treatment stop	

Measures in case of hematological toxicity during the inter-cycle interval (nadir):

 
-Febrile neutropenia* isolated
 
-Grade 4 neutropenia > 7 days
 
-Infection concomitant with grade 3-4 neutropenia
 
	
1st episode: reduce irinotecan dose to 120 mg/m^2
 
2nd episode: in addition reduce oxaliplatin dose to 60 mg/m^2
 
3rd episode: discuss further treatment reduction, maintain only LV5FU if necessary.

Grade 3-4 Thrombopenia	
1st episode: reduce the dose of oxaliplatin to 60 mg/m^2
 
2nd episode: in addition reduce the irinotecan dose to 150 mg/m^2 and reduce 5-FU IV continuous by 25 %. (If the irinotecan dose of patient is already at 150 mg/m^2, reduce to 120 mg/m^2 and reduce 5-FU IV continuous by 25%).
 
3rd episode: stop oxaliplatin and irinotecan, continue LV5FU

\*Definition: occurring during a period of medullar hypoplasia (PNN <500/mm3) with fever >38.5°C.

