**Hematologic DLT:**

- Grade 4 (NCI-CTCAE V5) neutropenia lasting > 3 days,
- Febrile neutropenia Grade 3 (ANC < 1,000/mm^3 with fever ≥ 38.5 °C) (CTCAE V5),
- Febrile neutropenia Grade 4 (life-threatening consequences; urgent intervention indicated),
- Grade 4 (NCI-CTCAE V5) anemia (i.e life-threatening consequences; urgent intervention indicated),
- Platelets < 25 000 /mm^3 or platelets < 50 000 /mm^3 associated with bleeding,
- INR or PTT elevation of Grade ≥ 3 (NCI-CTCAE V5) with associated bleeding,
- Grade ≥ 3 hemorrhage/bleeding events (NCI-CTCAE V5).

**Phase II:** 48-week disease-control rate (defined as the rate of non-progressing patients after central review, at 48-week post-initiation of therapy, to all treated patients.

Treated patients who have progressed or died before the 48-week evaluation will be considered as failure.

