**Table 5 : Dose modifications in case of digestive toxicities**

EVENTS	DOSE REDUCTION

 
-Isolated grade 3-4 diarrhea or
 
-Diarrhea + fever and/or grade 3-4 neutropenia
 
	
1st episode: reduce irinotecan to 120 mg/m^2
 
2nd episode: reduce oxaliplatin to 60 mg/m^2 and reduce 5-FU continue by 25 %
 
3rd episode: stop irinotécan

Recurrent diarrhea (>48 h) despite high doses of loperamide	No dose reduction for irinotecan, oxaliplatin and 5-FU after recovery except if grade 3-4 diarrhea, or diarrhea + fever and/or grade 3-4 neutropenia

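### Section 6.6 requires no FOLFIRINOX reduction after certain isolated phase I neutropenia DLTs, and its second-episode platelet nadir rule is unclear at irinotecan 120 and 180 mg/m²

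*Combined protocol and SAP*

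**What the plan says.** **DLT definitions (section 2.2.1, Hematologic DLT; phase I, first three cycles).** One febrile neutropenia DLT is "Febrile neutropenia Grade 3 (ANC < 1,000/mm 3 with fever ≥ 38.5 °C". Grade 4 neutropenia lasting more than 3 days is also a DLT.

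**FOLFIRINOX nadir triggers (section 6.6, inter-cycle block after Table 4).** Three neutropenia events take irinotecan to 120 mg/m² at the first episode: isolated febrile neutropenia, grade 4 neutropenia beyond 7 days, and infection together with grade 3-4 neutropenia. The footnote defines febrile neutropenia as "occurring during a period of medullar hypoplasia (PNN <500/mm3) with fever >38.5°C".

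**Other rules that can act on the same patient.** A D15 PNN below 1.5 × 10⁹/l delays treatment and takes irinotecan to 120 (Table 4). For grade 3-4 diarrhea, or diarrhea with fever and/or grade 3-4 neutropenia, Table 5 says "reduce irinotecan to 120 mg/m" (per square metre). The paragraph on other toxicities allows a reduction but does not require one. Table 9 interrupts regorafenib for grade 3 or 4 counts, with no dose change at the first two occurrences.

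**Second-episode platelet rules.** For a grade 3-4 nadir: "in addition reduce the irinotecan dose to 150 mg/m 2 and reduce 5-FU IV continuous by 25" percent. The exception begins "If the irinotecan dose of patient is already at 150 mg/m" and sends that patient to 120. For a second D15 platelet count below 100 × 10⁹/l, Table 4 says of irinotecan "reduce dose to 120 mg/m" (per square metre).

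**The concern.** An event that the protocol itself calls dose-limiting should lead to a defined action for the patient who had it. Here the DLT definition and the dose rule use different thresholds, so some DLT patients fall between them. Such a patient can receive the next FOLFIRINOX cycle at full dose without any departure from the protocol.

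The drug concerned is irinotecan. The background section reports that the SN-38 AUC rose 1.44-fold with regorafenib, and it makes stepwise irinotecan escalation and G-CSF conditions for combining the drugs. Systematic G-CSF on days 7 to 12 makes neutrophil recovery by D15 plausible, so the D15 rule may not catch these patients.

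The platelet rules raise a smaller problem. Two sites could read them differently for the same patient, or find that the stated dose is above the one the patient is on.

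What is at stake is patient safety and clear site instructions, not inference.

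**Working it through.** No sample size or error rate is involved. The check applies the written rules to cases.

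**1. Thresholds side by side**

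| Event | DLT (2.2.1) | FOLFIRINOX nadir trigger (6.6) | Gap |
|---|---|---|---|
| Febrile neutropenia, count | ANC <1,000/mm³ | PNN <500/mm³ | 500-999 |
| Febrile neutropenia, fever | ≥38.5 °C | >38.5 °C | exactly 38.5 °C |
| Grade 4 neutropenia, duration | >3 days | >7 days | more than 3 and up to 7 days |

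**2. Febrile neutropenia cases, temperature 38.6 °C.** Table 4's D15 limit of 1.5 × 10⁹/l equals 1,500/mm³.

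| ANC at nadir (/mm³) | Infection | Diarrhea | D15 PNN (/mm³) | DLT? | Required FOLFIRINOX reduction |
|---|---|---|---|---|---|
| 400 | no | no | 2,000 | yes | irinotecan 120 (febrile neutropenia row) |
| 500, 750 or 999 | no | no | 2,000 | yes | **none** |
| 500, 750 or 999 | no | no | 1,200 | yes | irinotecan 120 (Table 4) |
| 500, 750 or 999 | yes | no | 2,000 | yes | irinotecan 120 (infection row) |
| 500, 750 or 999 | no | yes | 2,000 | yes | irinotecan 120 (Table 5) |

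At exactly 38.5 °C, an ANC of 400 with no infection or diarrhea and a D15 PNN of 2,000 is also a DLT that misses the febrile neutropenia row.

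**3. Grade 4 neutropenia lasting more than 3 and up to 7 days.** With no fever above 38.5 °C, no infection or diarrhea, and recovery by D15, it is a DLT but meets no required trigger. Fever above 38.5 °C with PNN below 500 would bring in the febrile neutropenia row.

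Both gaps assume that no other rule applies; for example, a low platelet count would reduce oxaliplatin.

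**4. Size of the step not required (irinotecan to 120 mg/m²)**
- From 180 (DL2, DL3): 180 − 120 = 60; 60/180 = 33.3%.
- From 150 (DL-1, DL1): 150 − 120 = 30; 30/150 = 20.0%.
- Exposure ceiling: at most 24 phase I patients (section 10.1) × 3 DLT cycles = 72 patient-cycles, before replacements. This is an upper bound, not an expected count.

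**5. Second-episode platelet rules, irinotecan in mg/m²**

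| Current dose | Nadir rule | D15 rule |
|---|---|---|
| 180 | 150 | 120 |
| 150 | 120 | 120 |
| 120 | literally 150 | 120 (already there) |

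At 180 the rules differ by 150 − 120 = 30; the cuts are 30/180 = 16.7% and 60/180 = 33.3%. A patient whose second nadir has not recovered by D15, and whose D15 count is also a second low one, meets both rules in one cycle. At 120 the literal nadir dose is 150 − 120 = 30 above the current one.

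A dose of 120 can be reached before a second platelet nadir by four required routes: a first low D15 PNN, a first neutropenia nadir event, a second low D15 platelet count, or a first diarrhea event under Table 5.

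**The case against.** **DLT and dose rules serve different purposes.** One governs escalation and the other the care of an individual, so different thresholds are not in themselves an error. The patient also has safeguards: G-CSF, DLT reporting within 24 hours with possible sponsor measures (section 3.1), the D15 count gate, regorafenib interruption and the discretionary reduction. This stands in part. It makes harm less likely, but none of these safeguards requires a FOLFIRINOX reduction in the isolated, recovered case.

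**The gap is narrow.** This stands. A reader might infer that every febrile neutropenia DLT at ANC 500-999 goes without a reduction. The documents do not support that, because infection, diarrhea or an unrecovered D15 PNN each forces irinotecan to 120. Some sites may also classify fever with neutropenia as infection.

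**The platelet rules can be read sensibly.** A rule that says to reduce cannot mean to increase, and the D15 count comes after the nadir, so most clinicians would settle on 120. This largely stands. A reader might infer that a patient at 120 has no usable dose; the plain meaning of the verb answers that. Table 4 already has suitable wording for a second low PNN, "maintain dose at 120 mg/m" (per square metre), and the nadir rule lacks it. The 150 step after a recovered nadir may well be deliberate.

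**Notes may be missing.** Table 4 carries asterisk marks, including one at LV5FU, with no fitting note in the text as read. A reader might see a further conflict at the third episode, where the nadir rule says "stop oxaliplatin and irinotecan, continue LV5FU" and the D15 rule stops treatment. That cannot be sustained, because a lost note may govern that column. For the same reason, the absence of a precedence rule is claimed only for the text as read.

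**Conclusion.** The point holds in a limited form. An isolated phase I febrile neutropenia DLT at ANC 500-999, or an afebrile grade 4 neutropenia DLT lasting more than 3 and up to 7 days, has no required FOLFIRINOX reduction when there is no infection, diarrhea or other trigger and counts have recovered by D15. The step left to discretion is 60 mg/m² of irinotecan (33%) at 180, or 30 mg/m² (20%) at 150.

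The platelet nadir wording is secondary. It needs clarifying for a patient at 120 and, when both second-episode rules apply, for a patient at 180.

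The documents give no frequency for any of these cases, and they are probably uncommon. It would be wrong to count dose-by-episode combinations as a measure of how often the platelet rules disagree, because nothing says that nadir and D15 episodes are counted together.

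A reader might also infer a bias in DLT counts or in the 48-week disease-control rate. The documents do not support this: the DLT is recorded whatever the next dose is. Nor is grade 4 anemia part of the point, since the other-toxicities paragraph expressly exempts anemia. A wording amendment is worth making because it is cheap and concerns patient safety.

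**What to change.** Add three statements to section 6.6:

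1. Any neutropenia or febrile neutropenia event recorded as a phase I DLT triggers the first-episode irinotecan reduction to 120 mg/m².
2. No rule raises a dose; a patient already at 120 mg/m² stays at 120.
3. When several rules apply, the lowest resulting dose prevails.

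Leave the general nadir triggers unchanged for phase II, and keep the 150 mg/m² step for a recovered platelet nadir.

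The cost is a wording amendment. No extra visits or blood counts are needed, because the first statement acts only on events already recorded as DLTs. A more-than-3-day trigger in every cycle would be different: scheduled counts are on D1 and D8 in cycles 1 to 3 and only on D1 from cycle 4, so it would need added counts. The downside is an irinotecan dose lower by 20% to 33% in the few phase I patients who have such a DLT.

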**Table 5 : Dose modifications in case of digestive toxicities**

EVENTS	DOSE REDUCTION

 
-Isolated grade 3-4 diarrhea or
 
-Diarrhea + fever and/or grade 3-4 neutropenia
 
	
1st episode: reduce irinotecan to 120 mg/m^2
 
2nd episode: reduce oxaliplatin to 60 mg/m^2 and reduce 5-FU continue by 25 %
 
3rd episode: stop irinotécan

Recurrent diarrhea (>48 h) despite high doses of loperamide	No dose reduction for irinotecan, oxaliplatin and 5-FU after recovery except if grade 3-4 diarrhea, or diarrhea + fever and/or grade 3-4 neutropenia

**Table 6 : Dose modifications in case of Peripheral neuropathy:**

Toxicity	Duration of toxicity		
	≤7 days	>7 days and <14 days	Persisting between cycles
Paresthesia/dysesthesia without functional alteration (grade 1 NCI)	no modification	no modification	no modification
Paresthesia/dysesthesia with functional alteration not impacting activities of daily living (grade 2 NCI)	no modification	no modification	60 mg/m 
Paresthesia/dysesthesia with pain or functional alteration impacting activities of daily living (grade 3 NCI)	60 mg/m 	60 mg/m 	stop
Persistent paresthesia/dysesthesia, incapacitating	NA	NA	stop
Acute laryngopharyngeal dysesthesia	Prolong infusion duration to 6 hours.		

If oxaliplatin is stopped because of neurotoxicity, irinotecan and 5-FU should be continued.

**Table 7 : Dose modifications in case of other specific toxicities:**

Toxicity	Recommandations
Cardiac(angina pectoris or myocardial infarction)	Immediately and definitively stop 5FU
Alopecia	Refigerants helmets: - Not recommended with oxaliplatin (paraesthesia) - Not suitable in cases of bone metastases of the cranial vault
Extravasation (including oxaliplatin)	- Stop immediately the infusion - Do not remove the needle or catheter - Aspirate through the same needle maximum infiltrated product - Local ice Application ( 15-20 minutes every 4-6 hours for 72 hours ) - Local Corticosteroid - Check daily the infiltrated site - Surgical Opinion in doubt
Allergy to oxaliplatin	- Stop immediately the infusion of oxaliplatin - Infusion Polaramine / steroids - Filling solution for infusion ( macromolecules ) if necessary - Do not take the oxaliplatin infusion same day - Restart treatment with oxaliplatin for the next cure with: o Infusion of polaramine before oxaliplatin o Infusion of oxaliplatin during 6 h

#### **Recommendations in case of QT/QTc prolongation > 500msec:**

Oxaliplatin will be stopped. Patients will be referred to a cardiologist and monitored in a hospital with continuous cardiac activity recording performed until resolution to grade 1 or baseline.

#### **Recommendations in case of mucositis or hand-foot syndrome:**

These toxicities are caused by 5-FU. If grade 3-4 toxicity occurs, continuous 5-FU IV infusion will be reduced by 25% for the remaining cycles.

#### *Dose adaptation in case of bilirubin elevation:*

If bilirubin increase is > 1.5 ULN, it is preferable to postpone chemotherapy, because irinotecan is eliminated via biliary pathway, and check the presence of a tumoral relapse or obstruction of bile duct. Indication of chemotherapy will be retained if these two diagnoses are eliminated. However, it will be preferable to stop irinotecan if bilirubin elevation is persistent.

#### **Recommendations in case of Other toxicities:**

Other toxicities with > grade 2, except anemia and alopecia, may justify a dose reduction of 25%. If it is medically indicated, for instance, reduction of irinotecan to 120 mg/m^2 and/or oxaliplatin to 60 mg/m^2 and/or 5-FU decreased by 25 % in function of the type of toxicity.

## **REGORAFENIB**

**Table 8 : Dose modification/interruption for non-hematological adverse events related to regorafenib (except hand-foot skin reaction, hypertension, and liver function test abnormalities)**

Severity grade	Dose interruption	Dose reduction	Dose for subsequent cycles
Grade 0-2	No interruption of therapy	No change	No change
Grade 3	Interrupt therapy until toxicity resolves to Grade $\leq$ 2	Decrease dose by 40 mg (one tablet)	If toxicity remains $\leq$ Grade 2, dose re-escalation may be considered at the discretion of the investigator. If dose is re-escalated and toxicity ( $\geq$ Grade 3) recurs, institute permanent dose reduction
Grade 4	Interrupt therapy until toxicity resolves to Grade $\leq$ 2	Decrease dose by 40 mg (one tablet). Permanent discontinuation may be considered at the investigator's discretion.	—

a Excludes alopecia, non-refractory nausea/vomiting, non-refractory hypersensitivity, and non-clinically significant and asymptomatic laboratory abnormalities

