#### Non-Hematologic DLT:

- Missing > 7 days daily doses of regorafenib due to drug-related toxicity (scheduled treatment pause of regorafenib will not be counted),
- Grade  $\geq 3$  (NCI-CTCAE V5) non-hematologic toxicity, except:
  - Grade 3 nausea, vomiting, diarrhea and grade 2 alopecia
  - any untreated HFSR that can be adequately controlled with medical intervention,
  - Grade  $\geq 3$  lipase elevation without signs of pancreatitis,

- Grade ≥ 2 posterior reversible encephalopathy syndrome (PRES),
- Grade ≥ 2 retinopathy,
- Liver-specific DLTs are:
  - Drug-related gr. 3-4 bilirubin increase
  - Drug-related gr. 3-4 AST and/or ALT increase
  - Drug-related AST and/or ALT increase > 3 x ULN and associated with concurrent bilirubin increase(> 2 x ULN)

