**Table 10 : Dose modifications in case of drug-related liver function test abnormalities**

Observed elevations of ALT and/or AST	Occurrence	Recommended measures and dose modification
≤5 times upper limit of normal (ULN) (maximum Grade 2)	Any occurrence	Continue regorafenib treatment. Monitor liver function weekly until transaminases return to < 3 times ULN (Grade 1) or baseline.
> 5 times ULN ≤ 20 times ULN (Grade 3)	1st occurrence	Interrupt regorafenib treatment. Monitor transaminases weekly until return to < 3 times ULN or baseline. Restart: If the potential benefit outweighs the risk of hepatotoxicity, re-start regorafenib treatment, reduce dose by 40 mg (one tablet), and monitor liver function weekly for at least 4 weeks.
	Re-occurrence	Discontinue treatment with regorafenib permanently.
>20 times ULN (Grade 4)	Any occurrence	Discontinue treatment with regorafenib permanently.
>3 times ULN (Grade 2 or higher) with concurrent bilirubin >2 times ULN	Any occurrence	Discontinue treatment with regorafenib permanently. Monitor liver function weekly until resolution or return to baseline. Exception: patients with Gilbert's syndrome who develop elevated transaminases should be managed as per the above outlined recommendations for the respective observed elevation of ALT and/or AST.

Dose modifications and measures in case of hand-foot skin reaction (HFSR)/palmar-plantar erythrodysesthesia syndrome are provided in Table 11.

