**Table 11 : Dose modifications and measures for HFSR**

Skin toxicity grade	Occurrence	Recommended dose modification and measures
Grade 1	Any	Maintain dose level and immediately institute supportive measures for symptomatic relief.
Grade 2	1st occurrence	Decrease dose by 40 mg (one tablet) and institute supportive measures. If no improvement occurs despite dose reduction, interrupt therapy for a minimum of 7 days, until toxicity resolves to Grade 0-1. A dose re-escalation is permitted at the discretion of the investigator.
	No improvement within 7 days or 2nd occurrence	Interrupt therapy until toxicity resolves to Grade 0-1. When re-starting treatment, decrease dose by 40 mg (one tablet). A dose re-escalation is permitted at the discretion of the investigator.
	3rd occurrence	Interrupt therapy until toxicity resolves to Grade 0-1. When re-starting treatment, decrease dose by 40 mg (one tablet). A dose re-escalation is permitted at the discretion of the investigator.
	4th occurrence	Discontinue treatment with regorafenib permanently.
Grade 3	1st occurrence	Institute supportive measures immediately. Interrupt therapy for a minimum of 7 days until toxicity resolves to Grade 0-1. When re-starting treatment, decrease dose by 40 mg (one tablet). A dose re-escalation is permitted at the discretion of the investigator.
	2nd occurrence	Institute supportive measures immediately. Interrupt therapy for a minimum of 7 days until toxicity resolves to Grade 0-1. When re-starting treatment, decrease dose by 40 mg (one tablet).
	3rd occurrence	Discontinue treatment with regorafenib permanently.

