#### Termination of regorafenib :

In the event of gastrointestinal perforation or fistula develops

In the event of reversible Posterior Encephalopathy Syndrome (REPS)

-In the event of the appearance of cardiac ischemia and/or infarction, severe bleeding, severe hypertensive crisis

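### Regorafenib-related grade 2 retinopathy is dose-limiting, yet Table 8 continues regorafenib unchanged at grade 2 and allows restart after grade 3–4 while the event is still grade 2

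*Combined protocol and SAP*

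**What the plan says.** The synopsis and Section 2.2.1 both list "Grade ≥ 2 retinopathy" among the non-hematologic DLTs, provided it is drug-related and falls in the first three cycles.

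Regorafenib dosing after non-hematologic toxicity is governed by Table 8 in Section 6.6, whose title sets its scope: "Dose modification/interruption for non-hematological adverse events related to regorafenib (except hand-foot skin reaction, hypertension, and liver function test abnormalities". Its footnote removes a few further items, such as alopecia and non-refractory nausea or vomiting, but not retinopathy.

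The grade 0–2 row reads "No interruption of therapy", with no change of dose then or in later cycles. The grade 3 and grade 4 rows begin "Interrupt therapy until toxicity resolves to Grade" and set the restart level at grade 2 or lower, with a 40 mg reduction. After grade 3 the investigator may re-escalate if the toxicity stays at grade 2 or lower. At grade 4 the investigator may instead stop permanently.

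**The concern.** The protocol treats retinopathy as serious enough at grade 2 to count against a dose level, but at the same grade its dosing table tells the site to carry on at the same dose. A site that follows Table 8 literally gives the next scheduled regorafenib doses to a patient whose eye toxicity the protocol itself calls dose-limiting. After a grade 3 or 4 event, the site may restart regorafenib at a reduced dose before the event has fallen below the DLT threshold.

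What is at stake is the safety of the individual patient. Sample size, the 48-week disease-control analysis and the 3+3 counting rule are not affected.

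**Working it through.** The plan has no figure to reproduce here. The check sets the rules side by side.

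**1. Thresholds.** Inputs are the DLT list in Section 2.2.1 and Table 8 in Section 6.6.

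| Grade of regorafenib-related retinopathy | DLT in cycles 1–3 (phase I)? | Table 8 action |
|---|---|---|
| 1 | No | Continue, same dose |
| 2 | Yes | Continue, same dose |
| 3 | Yes | Hold to grade 2 or lower; restart 40 mg lower; re-escalation possible |
| 4 | Yes | Hold to grade 2 or lower; restart 40 mg lower; permanent stop optional |

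Table 8 first acts at grade 3, one grade above the DLT threshold of 2. Its restart level of grade 2 or lower includes a grade that still meets that threshold.

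**2. Is there an overriding rule?**
- The regorafenib termination list in Section 6.6 includes posterior reversible encephalopathy syndrome (PRES): "In the event of reversible Posterior Encephalopathy Syndrome (REPS". It does not include retinopathy.
- The other-toxicities paragraph, "Other toxicities with > grade 2, except anemia and alopecia, may justify a dose reduction of 25"%, starts above grade 2 and concerns chemotherapy doses.
- Table 12 is keyed to blood pressure. It can delay a dose for symptomatic hypertension, but not for retinopathy as such.
- Section 3.1 requires a DLT report within 24 hours and governs escalation. It sets no hold for the patient who had the DLT.

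None of these changes the Table 8 instruction at grade 2.

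**3. How are comparable DLTs handled?** Three toxicity-specific DLTs can be met below grade 3:
- PRES at grade 2 or higher: regorafenib is terminated (Section 6.6).
- Raised transaminases with raised bilirubin, in Table 10 ">3 times ULN (Grade 2 or higher) with concurrent bilirubin >2 times ULN": regorafenib is stopped permanently, Gilbert's syndrome excepted.
- Retinopathy at grade 2 or higher: no action at grade 2.

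So 2 of 3 have a permanent-stop rule, and 3 − 2 = 1 has no action at its own threshold. By contrast, a first grade 2 hand-foot skin reaction, which is not a DLT by grade alone, gets "Decrease dose by 40 mg (one tablet) and institute supportive measures" (Table 11).

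**4. Exposure.** Regorafenib is given on days 4 to 10, so 10 − 4 + 1 = 7 doses per cycle. For a persisting grade 2 event, Table 8 withholds 0 of those 7.

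The DLT window is the first 3 cycles, in phase I only (Section 5.1, footnote 14). Of the 12 planned combination cycles, 12 − 3 = 9 lie outside it, as does any regorafenib maintenance (Section 6.4). Of the 69 phase II patients, 69 − 6 = 63 enter after phase I and are never in the DLT reporting channel.

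**5. Size of the cut on restart.** Relative to the planned doses, 40 mg is 40/160 = 25%, 40/120 = 33% or 40/80 = 50%.

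**The case against.** The strongest reply is that a DLT threshold and a dosing threshold serve different purposes. DLTs drive cohort expansion, the maximum tolerated dose and the recommended phase II dose (Section 3.1). Nothing in the documents says that every DLT must trigger a hold in that patient. This stands as a general principle. It does not explain why the other two DLTs reachable below grade 3 have patient-level stop rules and retinopathy does not, and the documents offer no reason for the difference.

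A reader might also infer four stronger things that the documents do not support:
- **Full-dose restart after grade 3 or 4.** Table 8 requires a 40 mg cut in both rows and offers a permanent stop at grade 4.
- **No protection at all.** Section 6.1 makes further cycles conditional on the absence of unmanageable toxicity. Section 9.1 lets the patient, investigator or sponsor stop treatment at any time. In phase I the sponsor also sends dosing information and safety measures to sites (Section 3.1). Later events are still recorded with grade, causality and action taken (Section 11.1.2), and can be reported as serious if judged medically relevant (Section 11.2.1). These safeguards are real, but they rest on judgement or reporting, against a written default to continue.
- **Every retinopathy DLT is affected.** Table 8 applies only to events attributed to regorafenib, whereas a DLT may be related to any drug in the combination.
- **Grade 2 retinopathy necessarily limits daily activities.** Section 11.1.3 gives a general guideline in which that is one of several grade 2 descriptors. The event-specific criteria belong to the CTCAE, so the clinical weight of grade 2 retinopathy cannot be settled from the protocol body.

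**Conclusion.** The point holds for retinopathy attributed to regorafenib: Table 8 has no action at the grade the protocol calls dose-limiting, and its restart and re-escalation levels include that grade. It is a stated rule with the less safe default, not merely a missing detail, and it should be corrected in the next amendment.

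The conclusion assumes that sites apply Table 8 as written and that the event is attributed to regorafenib. The documents give no incidence for retinopathy, so the number of patients affected cannot be computed; that it is small is an assumption.

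**What to change.** Add retinopathy to the exceptions in the Table 8 title and give it its own rule for all cycles of both phases, maintenance included: at grade 2 or higher (so also grades 3 and 4), interrupt regorafenib until grade 1 or lower, then restart 40 mg lower or stop. Grade 1 is the level just below the protocol's own DLT threshold. The exact restart condition is a clinical choice that the documents do not settle, and the clinical team should confirm it.

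A persisting event would then receive no regorafenib. Section 9.1 already lists an interruption beyond 28 days as a reason to discontinue, subject to discussion with the sponsor where there is clinical benefit.

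The cost is one table entry, slightly lower dose intensity in the few patients affected, and an eye re-check for each of them, because the visit schedule in Section 5.1 contains no eye assessment. The change does not add detection of new cases. Sample size is unchanged. Inside the DLT window, a hold that misses more than 7 days of regorafenib is itself a DLT, but that patient already counts as having one, so the 3+3 tally does not move.
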